#### ***4.2.1 Model development***

The entire cohort is randomly divided into two datasets: a training cohort (80%), which will potentially be utilized for training twelve machine learning models and optimizing their parameters, and an internal validation cohort (20%), which was employed to evaluate the developed models on unseen data and refine the hyperparameters.

The variable selection process in the development sample will be conducted using a recursive feature elimination (RFE) algorithm. RFE ranks the most relevant predictors in a dataset by training models with and without all potential predictor combinations. To identify the optimal number of variables, we will assess the incremental gain in predictive performance associated with each variable and stop at the inflection point. RFE is an iterative process that starts with all possible features in the dataset and progressively removes the least relevant features, building a model after each iteration. The goal is to find the optimal subset of features that maximizes the predictive power of the model. In each iteration, RFE evaluates the performance of the model with and without a specific feature and removes the feature if its removal results in a significant improvement in model performance. This process is repeated until the

desired number of features is reached or a stopping criterion is met. The inflexion point is the point at which the incremental gain in predictive performance begins to decrease significantly. Identifying the inflexion point helps to ensure that the final model does not overfit the data and can generalize well to new data. In conclusion, by using the RFE algorithm and identifying the inflexion point, the development sample will undergo a thorough variable selection process, ensuring that the final model is as predictive as possible while avoiding overfitting.

After variable selection with RFE, we will be trained potential seven statistical models with centred and scaled selected predictors because of the different scales of the predictors and to ease the intercept of models to the IAPI, including a logistic regression, decision tree, random forest, artificial neural network (ANN), eXtreme Gradient Boosting algorithm (XGBoost), support vector machine (SVM), k-nearest neighbors (k-NN). Logistic regression is suitable for binary classification problems, while decision trees can handle both binary and multi-class problems. Random forests and XGBoost are based on decision trees and are known for their good performance in predicting both continuous and categorical variables. ANNs can be used for nonlinear problems, but they require more time for training. SVM and k-NN are also popular for classification problems, but they require different preprocessing techniques.

To evaluate the performance of each model, we will be using the cross-validation. With k-fold cross-validation, the data is randomly divided into k subsets, and each model is trained on k-1 subsets and tested on one subset. This process is repeated k times, with each of the k subsets being used once as the test set. The average

performance across all k tests is then used as the final performance measure. To assess the degree of potential over-fitting of each algorithm, we will be trained them using a 10-fold 10-repeat cross-validation procedure.

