### **Methods:**

We will use a pre-set observational assessment scale that consists of 24 indicators to construct the predictive model in this study. In addition to these pre-set indicators, the researchers will also collect other relevant indicators that they believe may contribute to the predictive model. Primary outcome was incidence of IAPI of any stage at 7 days from operating room admission. Secondary outcomes were in-hospital mortality (follow-up endpoint is 3 months after surgical procedure), surgical complication, and hospitalization costs. The prospective cohort study dataset is divided randomly into two

subsets: a training group (80% of the data) and an internal validation group (20% of the data). The training group is used for model development, while the internal validation group remains untouched until later stages. In model development, researchers can explore different variables and test various machine learning algorithms, such as logistic regression, artificial neural network (ANN), XGBoost, support vector machine (SVM), k-nearest neighbors (k-NN), naive Bayes, gradient boosting machines (GBM), AdaBoost, Gaussian mixture model (GMM), and support vector regression (SVR). They can train and optimize these models using the training dataset. After training the models on the training dataset, researchers can evaluate their performance using appropriate evaluation metrics (e.g., accuracy, precision, recall, F1-score, area under the receiver operating characteristics curve). Based on the evaluation results, we refine the model by tweaking hyperparameters, feature selection, or employing techniques like cross-validation or grid search. This iterative process aims to find the best-performing model configuration. Once the model is optimized using the training dataset, it is then evaluated on the internal validation dataset. This evaluation serves as an unbiased assessment of the model's performance on unseen data, providing an estimate of its ability to generalize. Based on the performance on the internal validation dataset, to choose the best-performing model as the final predictive model.

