## 4. Data Analysis

### 4.1 Sample size

The primary outcome of this study is IAPI in patients who underwent surgery procedure.

The fixed position of surgical patients in the surgical procedure, and the occurrence of IAPI risk is time-dependent, which it is positively correlated with the advancement of time and the occurrence of IAPI events in surgical patients. For time-to-event outcomes, ensure the sample size is enough to: Estimate the overall outcome proportion with sufficient precision at one or more key time-points in follow-up; Target a shrinkage factor of 0.9; Target small optimism of 0.05 in the apparent  $R^2_{\text{Nagelkerke}}$ . The formula provided by Riley et al. is as follows:

Time-event-outcome, the sample size (number of participants, n) required to achieve the expected uniform contraction coefficient S can be expressed as:

$$n = \frac{P}{(S-1)\ln\left(1 - \frac{R_{cs}^2}{S}\right)}$$

To calculate the sample size, to ensure that the expected optimistic value of  $R^2$  (i.e.,  $R_{cs}^2/\max(R_{cs}^2)$ ) has a smaller expected optimism. For time-event-outcome, the first step is to calculate the contraction coefficient corresponding to the expected optimistic value in  $R^2_{\text{Nagelkerke}}$ :

$$S = \frac{R_{cs}^2}{R_{cs}^2 + \delta\max(R_{cs}^2)}$$

The recent randomized controlled trial results showed an incidence of IAPI (stage I and above) of 13.9%, assuming 0.05 acceptable difference in apparent & adjusted

R-squared. The study used the R4.1.2 software (pmsampsize package) to estimate the minimum sample size required to develop the new model. Minimum sample size required for new model development is 4115, with 572 events (assuming an outcome prevalence = 0.139) and an Events per Predictor Parameter (EPP) is 23.83. In addition, according to the pre-model design requirements, the total sample was divided into 80% samples for the development of the new model and 20% samples for the validation of the model. This means that a total of 5144 cases are required. Considering a possible 10% loss of follow-up, the minimum sample size required for the prediction model was 5658 cases.

```
NB: Assuming 0.05 acceptable difference in apparent & adjusted R-squared
NB: Assuming 0.05 margin of error in estimation of intercept
NB: Events per Predictor Parameter (EPP) assumes prevalence = 0.139
```

	Samp_size	Shrinkage	Parameter	CS_Rsq	Max_Rsq	Nag_Rsq

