#### **4.2 Data analysis**

This study is divided into two distinct sections. The aim of the first part is to create and validate a IAPI risk score for individuals from the whole cohort, predicting their individual IAPI values using a combination of potential predictive variables. The aim of the second part is to evaluate whether the IAPI score is helpful in predicting 90-day mortality in individuals from the whole cohort. We also evaluated the incidence and attributable mortality to IAPI, SSI, and surgical complications in patients admitted for

surgical procedures during the same study period.

All statistical analyses were performed with R (the latest version; R Foundation for Statistical Computing) and Python (the latest version; Python Software Foundation). All tests conducted in this study were 2-tailed, and  $P < 0.05$  was deemed statistically significant.

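### The 20% internal validation set is also used to refine hyperparameters and to choose the final model, so its AUC is modestly optimistic on average and not the unbiased estimate the plan claims

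*Combined protocol and SAP*

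**What the plan says.** - **Split.** Section 4.1 divides everyone: "the total sample was divided into 80% samples for the development of the new model and 20% samples for the validation of the model". Neither section 4.1 nor section 4.2 describes a third set or an external cohort.
- **Aim.** Section 4.2 sets the first aim as "to create and validate a IAPI risk score for individuals from the whole cohort", so validation is part of the study's purpose.
- **Tuning, abstract (Methods).** At the training stage, "we refine the model by tweaking hyperparameters", with cross-validation or grid search among the techniques named. The 20% set comes in only after this, "while the internal validation group remains untouched until later stages".
- **Tuning, section 4.2.1.** The 20% cohort is the one "which was employed to evaluate the developed models on unseen data and refine the hyperparameters".
- **Claim and choice, abstract.** "This evaluation serves as an unbiased assessment" of performance on unseen data. The next sentence reads: "Based on the performance on the internal validation dataset, to choose the best-performing model as the final predictive model".
- **Reporting, section 4.2.2.** The AUC comes from this same cohort, with a 2,000-draw bootstrap interval, and all models are compared with five existing scales. No step repeats the tuning or selection.
- **Cross-validation, section 4.2.1.** 10-fold, 10-repeat cross-validation is planned to evaluate the models and gauge over-fitting. Of k-fold cross-validation in general the section says that the average "performance across all k tests is then used as the final performance measure". It is not named as the rule for choosing the model.
- **Logistic regression, section 4.2.4.2.** It is described favourably because it yields a points score, but it is not fixed as the final model.

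**The concern.** A held-out set gives an unbiased estimate only for a model that was fixed without it. If hyperparameters are refined on those patients, or the winner is the model that did best on them, part of the winner's advantage is chance in that sample. The same chance is then reported as performance.

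Two pairs of statements cannot both stand. The unbiasedness claim conflicts with choosing or refining on that cohort. Tuning on training data (abstract) conflicts with refining on validation data (section 4.2.1).

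At stake are the headline AUC, its interval, and the comparison with the Braden, Waterlow, Norton, Cubbin & Jackson and Munro scales. Those scales are fixed in advance and gain nothing from selection, so the bias favours the new model. The plan also leaves unclear whether the validation AUC or the cross-validation average is the primary figure.

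**Working it through.** **1. The plan's own figures (section 4.1).** n = P / [(S − 1) ln(1 − R²/S)], with P = 24, S = 0.900 and Cox-Snell R² = 0.051:
24 / [(−0.1) × ln(1 − 0.051/0.9)] = 24 / 0.0058336 = 4114.1, rounded up to 4,115 as printed. The maximum R² at prevalence 0.139 is 0.5535 (printed 0.553). 4,115 / 0.8 = 5143.75, so 5,144. All reproduce.

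**2. Size of the validation set.** 5,144 × 0.2 = 1028.8, about 1,029 patients. 1028.8 × 0.139 = 143.0 events, leaving 886 non-events.

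**3. Precision of the AUC.** The plan gives no expected AUC. Assuming a normal linear predictor, R² = 0.051 at prevalence 0.139 needs a linear-predictor SD of 0.691, which implies an AUC A of about 0.683. Hanley-McNeil variance:
[A(1 − A) + (143 − 1)(A/(2 − A) − A²) + (886 − 1)(2A²/(1 + A) − A²)] / (143 × 886)
= (0.2165 + 7.40 + 77.76) / 126,698 = 0.000674.
SE = 0.026; 95% half-width = 1.96 × 0.026 = 0.051.

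**4. Choosing the best of K models.** If the models are equally good and their AUC estimates have common correlation ρ, the expected excess is SE × √(1 − ρ) × E[maximum of K standard normals]. That last term is 1.35, 1.54 and 1.63 for K = 7, 10 and 12, the counts found in the text. Example: 0.026 × √0.2 × 1.35 = 0.0157. Unequal models were simulated, with each true AUC falling short of a common ceiling by a half-normal amount. Selection is by highest validation AUC. Bias for K = 7 / 10 / 12:

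| True AUCs | ρ = 0.8 | ρ = 0.9 |
|---|---|---|
| Equal | 0.016 / 0.018 / 0.019 | 0.011 / 0.013 / 0.013 |
| Half-normal SD 0.02 | 0.012 / 0.014 / 0.015 | 0.008 / 0.009 / 0.010 |
| Half-normal SD 0.04 | 0.010 / 0.011 / 0.012 | 0.006 / 0.007 / 0.008 |

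Over the whole table, coverage of the nominal 95% interval runs from 90.6% to 94.7%. In the worst cell (equal models, ρ = 0.8, K = 12) the interval lies wholly above the truth about 9.3% of the time and wholly below it about 0.2%, against 2.5% each.

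**5. Another selection metric.** The abstract says only best-performing and lists accuracy, precision, recall, F1-score and AUC as examples. If the metric used has an assumed correlation of 0.5 with the AUC error, the bias is about halved: 0.5 × 0.006 = 0.003 up to 0.5 × 0.019 = 0.0095.

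**6. Refining hyperparameters on the cohort.** For one algorithm over 5 to 20 equally good settings at an assumed ρ of 0.95, the bias is 0.007 to 0.011. If 10 settings for each of 7 to 12 models are all compared there (70 to 120 candidates), the same formula gives 0.019 to 0.030 at ρ 0.8 to 0.9, and about 0.014 to 0.047 over ρ 0.95 down to 0.5.

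**7. After the fix.** With the model locked on training data, direct simulation gave mean error between −0.0007 and +0.0004 (Monte Carlo SE 0.0004), that is, zero.

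**The case against.** The best defence is that each use of the cohort rests on one sentence. Choice on validation performance appears only in the abstract, and section 4.2 has no such rule. Refining on validation data appears only in section 4.2.1, while the abstract puts tuning before the cohort is opened. Reading the abstract in the plan's favour removes the tuning problem but not the choice. Reading section 4.2.1 alone removes the choice but not the tuning. No reading of the text as it stands clears both.

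Several limits on the point do stand:

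- Keeping the set untouched until later stages does not exclude a later use, so that phrase is not itself a contradiction.
- A reader might infer that the 20% set gives the only out-of-sample estimate. It does not: the planned cross-validation also gives out-of-fold estimates. The text does not say that variable selection is repeated inside the folds, which could affect those estimates but not the validation AUC.
- A reader might infer a specific inflated error rate for declaring the model better than a scale. The plan names no test for that comparison, only a general two-sided 5% level, so any such rate is hypothetical. Only the direction of the bias is established.
- Section 4.2.4.2 leans towards logistic regression. If it were fixed in advance without tuning, the bias would be near zero, but the plan does not fix it.

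**Conclusion.** The point holds, at modest size. Under the current text the chosen model's validation AUC is optimistic on average, and the description of it as unbiased is wrong.

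The range of about 0.006 to 0.019 for best-of-7-to-12 selection rests on selection by AUC, correlations of 0.8 to 0.9, and true AUCs between equal and half-normal SD 0.04. The documents supply none of these, so the size is uncertain. It falls with another metric or a clearly superior model, and rises if many settings are also tried on the cohort.

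A reader might infer that the validation result is worthless or that every reported AUC will be too high. Neither follows. The selection bias is well under the 0.051 half-width, and in individual samples the chosen model's AUC can still fall below its true value. This should be fixed before analysis, but it does not threaten the study's design.

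**What to change.** 1. **Section 4.2.1, split.** Replace the clause on the validation cohort's use with:
   > which will be used only after the final model is locked, to evaluate it on unseen data
2. **Abstract, last sentence of Methods.** Replace with:
   > Hyperparameters and algorithm will be chosen by highest mean AUC-ROC in 10-fold 10-repeat cross-validation within the 80% training set, with variable selection repeated in each fold so that candidates are compared fairly; the one locked model is then evaluated once on the internal validation set.
3. **Section 4.2.1, cross-validation.** State that the cross-validation average is the selection tool. Give one list of candidate models: the abstract lists 10, while section 4.2.1 says twelve and then seven.
4. **Section 4.2.2.** Make the locked model's AUC on the 20% set, with its bootstrap interval, the primary estimate and the basis for comparison with the five scales. Other models may still be shown as descriptive but cannot change the choice.
5. **Section 4.2.4.2.** State whether logistic regression is fixed in advance or is one candidate.

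The cost is wording and computing time; no new patients or data are needed. The reported AUC will probably be slightly lower, and the validation data can no longer inform the choice of model.

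### Section 4.2.1 gives conflicting RFE elimination rules, and its 10 × 10 cross-validation leaves out the selection step, so over-fitting is understated

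*Combined protocol and SAP*

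**What the plan says.** Section 4.2.1 (Model development) confines selection to the 80% sample: "The variable selection process in the development sample will be conducted using a recursive feature elimination (RFE) algorithm". It then describes elimination and stopping in several ways:

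- **By rank:** the algorithm "progressively removes the least relevant features, building a model after each iteration".
- **By improvement:** at each iteration it compares the model with and without a feature and "removes the feature if its removal results in a significant improvement in model performance".
- **By the performance curve:** "we will assess the incremental gain in predictive performance associated with each variable and stop at the inflection point".
- **By an open criterion:** the process runs until the "desired number of features is reached or a stopping criterion is met".

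No performance metric, test, tolerance or target number is given for any of these.

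The order of work is also stated: "After variable selection with RFE, we will be trained potential seven statistical models with centred and scaled selected predictors". To judge over-fitting of each algorithm, "we will be trained them using a 10-fold 10-repeat cross-validation procedure". The average over the folds is named as the final measure of performance. Nothing says that RFE is repeated within folds.

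Section 4.2.2 (Model assessment) evaluates AUC in the 20% internal validation cohort. Section 4.2.1 also uses that cohort to refine hyperparameters, and the Methods part of the Abstract uses it to choose the final model.

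**The concern.** There are two separate problems.

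**Conflicting rules.** A predictor that contributes nothing usually leaves performance almost unchanged when it is dropped. A rule that removes it on a significant improvement will therefore tend to keep it, whereas a rank-based rule with an inflection stop would drop it. Two analysts could follow the same section and reach models of very different length. The study wants a simple tool, and the Introduction criticises the Munro scale because its 15 indicators take too much staff time. Table 1 also repeats constructs: mobility is item 4, 14, 21, 27 and 37, and age is item 8, 23 and 36. Removing one of several near-duplicates costs little but would seldom help significantly.

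**Selection outside the cross-validation.** RFE has already used the outcomes of every patient who later sits in a left-out fold. The cross-validation then measures over-fitting of the coefficients but not of the choice of variables, so its average is biased upwards.

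**Working it through.** **Step 1: reproduce the plan's figure, to calibrate the check.** Section 4.1 gives 24 parameters, shrinkage 0.9, Cox-Snell R² 0.051 and prevalence 0.139. The formula is n = P / ((S − 1) ln(1 − R²/S)).

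- 24 / ((0.9 − 1) × ln(1 − 0.051/0.9)) = 4114.1, rounded up to 4115, as stated.
- Events: 4115 × 0.139 = 572. Events per parameter: 572/24 = 23.83, as stated.

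The plan gives no figure for RFE or for cross-validated performance, and neither problem has a closed form. Both were simulated.

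**Step 2: inputs.** From the documents: n = 4115, prevalence 0.139, R² about 0.051. Two-sided 0.05 is the general rule in section 4.2 and is not tied to RFE. Assumptions not in the documents: logistic regression; independent normal predictors; 10 true predictors of equal effect (log-odds 0.218 per SD, intercept about −1.99); and 40 or 90 noise candidates. The candidate number is uncertain because section 4.1 uses 24 parameters, while Table 1 lists 50 numbered items plus an open item 51.

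**Step 3: the quoted removal rule, literally and alone.** Features were removed one at a time while removal gave a significant improvement (paired test on 10-fold cross-validated log-loss, two-sided 0.05). In 25 runs with 10 true and 40 noise candidates:

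- Noise predictors kept: mean 763/25 = 30.5 of 40, or 76% (range 23 to 36).
- True predictors removed: none in any run.

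Rank-based RFE stopped at 10 variables kept 0.13 noise predictors on average (30 runs). That stop equals the true number, so it favours the rank rule. Stopped at 15, it must keep at least 5, and it kept exactly 5.0. A second simulation of the quoted rule, with 51 candidates of which 41 were noise (131 datasets), kept 30 of the 41.

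**Step 4: cross-validation after selection and with selection inside the folds.** Rank-based RFE to a fixed size; true AUC from a large independent sample.

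| Candidates, kept (runs) | RFE before CV | RFE inside folds | True AUC | Before minus true |
|---|---|---|---|---|
| 50, keep 10 (30) | 0.6811 | 0.6797 | 0.6777 | 0.0034 |
| 50, keep 15 (30) | 0.6849 | 0.6738 | 0.6720 | 0.0129 |
| 100, keep 20 (31) | 0.6855 | 0.6605 | 0.6657 | 0.0198 |

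The SD of the first AUC column is 0.0126 in the 50-candidate settings, so its Monte Carlo standard error is 0.0126/√30 = 0.0023. The smallest excess is therefore not clearly different from zero; the other two are. Selection inside the folds lands within about 0.005 of the truth in all three settings (+0.0020, +0.0018, −0.0052).

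In the 100-candidate setting, an untouched 20% hold-out of 1029 patients gave a mean AUC of 0.6687, against a truth of 0.6657.

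A further simulation (51 candidates, keep 10, 33 datasets) gave 0.672 before, 0.660 inside and 0.660 true, an excess of 0.012. Its signal strength is not stated and was probably weaker than the plan's.

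**The case against.** **The plan need not keep useless predictors.** The sentence says a feature is removed *if* removal helps significantly, not *only if*. It sits in a general description of RFE, while the forward-looking commitment is the inflection-point stop, which the section's conclusion repeats. A reader might infer that the plan will retain most useless predictors. The documents do not support that, because rank-based removal with an inflection stop would prune noise if applied. The conflict does stand: the section contains both kinds of rule and gives nothing by which to choose.

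**The 76% rests on inputs the plan does not supply.** The test, the loss, the noise share and the independence of predictors are all assumed. Table 1 items come from established risk scales and overlap, and section 4.2.4.1 plans to harmonise their definitions. No other noise share or correlation was tried. This stands, so the figure illustrates direction and rough size only.

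**Over-fitting is checked elsewhere.** A reader might infer that it is hidden altogether. It is not: RFE does not use the 20% cohort, and section 4.2.2 assesses AUC there. In simulation an untouched hold-out recovered the truth. That protection is weakened because the same cohort is used for tuning and for choosing the final model. Section 4.2.1 also still labels the fold average as the final measure.

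**The bias is modest.** This is correct at this sample size for logistic regression. It grows with the candidate pool and the number of variables kept; correlated items and flexible learners were not simulated.

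**Conclusion.** The point holds in a limited form. The elimination and stopping rules in section 4.2.1 contradict each other. One of them, read literally and alone, kept about three quarters of pure-noise candidates under the stated assumptions, contrary to the aim of a simple score.

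The 10 × 10 cross-validation omits selection. Its average AUC is too optimistic by about 0.003 to 0.02 over the settings tried, with the lower end within simulation error. Over-fitting is understated, not concealed, because RFE does not use the 20% cohort.

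This should be corrected before analysis: choosing between conflicting rules after seeing the data would add optimism that no cross-validation captures.

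**What to change.** 1. Delete the sentence on significant improvement and state a single rule. For example: drop the lowest-ranked predictor at each step, then keep the smallest set whose cross-validated log-loss (or AUC) is within a pre-set tolerance of the best. One standard error is a common tolerance. An explicit numeric definition of the inflection point would serve equally well.
2. Name the metric, the tolerance and the model used for ranking.
3. State that the whole of RFE, with centring, scaling and tuning, is repeated inside every training fold of the 10 × 10 cross-validation, and that performance is computed on the left-out fold only.

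The cost is a few sentences in the SAP and more computing, since selection and tuning run on 10 × 10 = 100 training sets instead of once. The reported cross-validated AUC will be slightly lower: in the simulations by 0.0014 (0.6811 − 0.6797), 0.0111 (0.6849 − 0.6738) and 0.0250 (0.6855 − 0.6605). No extra patients or data are needed.
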